#### **4.Gross motor performance.**

The impairment in CP, including secondary impairments such as spasticity, muscle contracture, bone deformity, muscle weakness, and coordination disorders, is multifactorial and primarily affects the lower extremities, such as deficits in walking ability (29).

The varying levels of impairment affecting children with CP can be described according to the Gross Motor Classification System. Physical inactivity in children with CP increases the risks of secondary problems such as pain, depression, social isolation, fatigue, pressure sores, and mobility limitations. Children with CP suffer from motor and cognitive disabilities, which usually require a long-term, multifaceted, and multidisciplinary approach (30).

Children with CP also tend to have lower endurance, muscular strength, and cardiorespiratory fitness than the general population. The consequences of chronic muscle imbalance and the resultant deformities can cause increasing disability with age. One of the most significant problems faced by children with

CP is defective postural control. Maintaining postural control, which is required to perform activities of daily living, is often a major challenge for children with CP (31).

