## **5.Balance.**

Spastic diplegia, the most prevalent type of CP, is characterized by a wide range of ambulatory outcomes. It affects bilateral lower extremities more than upper extremities in most cases. As a result, walking function and corresponding balance control are impacted (32).

Balance control is important in the performance of most functional skills. Postural balance control in children with CP deteriorates as compared to typically developing children, most likely due to slowed and impaired development of neural motor control mechanisms together with the common secondary musculoskeletal abnormalities (33).

Balance control plays a central role in the motor dysfunction in children with spastic diplegic cerebral palsy. Reduced ability of children with spastic diplegia to adapt the sensory and motor components of postural control to changing task and environmental demands affects their proper response to balance disturbance, the recovery from unexpected threats to stability that refer to reactive balance control, functional deficits and the subsequent limitations in mobility. The amount of time required to recover stability following a balance threat (time of stabilization) and the mean area of centre of mass (COM) displacement per second during balance recovery are increased in these children (34).

Due to poor postural control, the delineation “walking by falling” is especially true for children with CP. A heightened fear of falling can also lead to restriction of activities. Although not all falls can be prevented, those due to poor postural control can be reduced by improving balance performance (35).

Falls may result in pain, injury and disability, and individuals may lose confidence in their ability to perform routine activities. Because a relation has been established between constraints on balance control and functional limitations in children with CP, increased efficiency of postural balance control may be necessary for them to facilitate functional performance (36).

Therefore, many researchers have suggested that balance training should be a crucial component of any rehabilitation program for these children. Such training can modify postural balance control by modulating the amplitude of muscle activities and speeding recruitment of the postural muscles (37).

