## **6. Gross Motor Function Measure 88 (GMFM-88).**

The GMFM is used by a variety of rehabilitation specialists for clinical and research purposes to measure change over time, and the effectiveness of interventions to affect change (39).

The standardized measures provide objective information in an easy-to-understand format. As stated earlier, the GMFM has become the standard tool for measuring change in gross motor function over time for children with CP. Given its unique purpose, its wide use, and the amount of research that has been conducted using this outcome measure, examining the usefulness as related to intervention is important to measure change over time for children with CP. The Gross Motor Function Measure (GMFM) and its subsequent revisions, has become the most common functional outcome measure used by rehabilitation specialists to measure gross motor functioning in children with CP and other

neurologically based conditions, such as Down syndrome and traumatic brain injury (40).

This tool showed high validity at 0.91 when applied, the GMFM-88 was reported to be a useful method for measuring gross motor function in children with CP because of its high reliability, with inter-rater reliability of 0.77, test–retest reliability of 0.88, and intra-rater reliability of 0.68 (41).

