#### **Sample size calculation:**

Using G-power version 3.1.9.7 for windows and regarding t-test study, alpha level of 0.05, confidence interval 80% and effect size of 1.135 calculated from the previous study of Krishna et al. (43), the total sample size will be 28 children (fourteen in each group), (Figure 1). We will increase number to be 30 children (Fifteen in each group) to avoid any drop out.

To avoid selection bias, the children will be randomly allocated by simple random method via choosing one of two wrapped cards representing the two treatment groups, which are:

- Group (A): will receive virtual reality in addition to the traditional exercise program.
- Group (B): will receive traditional exercise program.

[figure not shown]
[figure not shown]

Figure 1: Sample size calculation in G-power software program.

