## **B. Assessment procedures**

### **1. Evaluation of gross motor performance using GMFM-88:**

The Gross Motor Function Measure (GMFM) 88 will be used to determine the severity of each case and to assess the child's motor performance in five dimensions: lying and rolling (17 items); sitting (20 items); crawling and kneeling (14 items); standing (13 items); and walking, running, and jumping (24 items). All items will be checked and scored before interpretation of child's performance in each dimension. Scores of each dimension will be expressed as percentage of maximum scores for that dimension. Total score will be obtained by averaging percentage scores across the 5 dimensions. Individual dimensions of GMFM-88 can be administered depending on the child's current level of function (41).

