#### **B. Statistical analysis**

For testing the study hypotheses, the following statistical methods will be used:

1. Descriptive statistics (mean and standard deviation) of the demographic data of all patients in both groups.
2. The suitable statistical tests will be used according to the nature of the collected data.
3. Level of significance for all tests will be set at  $p\text{-value} \leq 0.05$ .
4. The statistical package for social sciences (SPSS) version 26 for windows (Armonk, NY: IBM Corp) will be used for data statistical analysis.

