#### Contact for Research Group:

CanChild Centre for Childhood Disability Research,  
Institute for Applied Health Sciences, McMaster University,  
[name],  
[name]  
Email: [[contact]](mailto:[contact]) Website: [www.canchild.ca](http://www.canchild.ca)

GMFCS level is a rating of severity of motor function. Definitions for the GMFCS-E&R (expanded & revised) are found in Palisano et al. (2008). *Developmental Medicine & Child Neurology*. 50:744-750 and in the GMAE-3 scoring software. <http://motorgrowth.canchild.ca/en/GMFCS/resources/GMFCS-ER.pdf>

Check (3) the appropriate score: if an item is not tested (NT), circle the item number on the right column

| Item                     | A: LYING & ROLLING  | SCORE                      |                            |                            |                            | NT  |
|--------------------------|---|----------------------------|----------------------------|----------------------------|----------------------------|-----|
| 1.                       | SUP, HEAD IN MIDLINE: TURNS HEAD WITH EXTREMITIES SYMMETRICAL .....           | 0  | 1  | 2  | 3  | 1.  |
| * 2.                     | SUP: BRINGS HANDS TO MIDLINE, FINGERS ONE WITH THE OTHER.....                 | 0  | 1  | 2  | 3  | 2.  |
| 3.                       | SUP: LIFTS HEAD 45° .....   | 0  | 1  | 2  | 3  | 3.  |
| 4.                       | SUP: FLEXES R HIP & KNEE THROUGH FULL RANGE .....                             | 0  | 1  | 2  | 3  | 4.  |
| 5.                       | SUP: FLEXES L HIP & KNEE THROUGH FULL RANGE.....                              | 0  | 1  | 2  | 3  | 5.  |
| * 6.                     | SUP: REACHES OUT WITH R ARM, HAND CROSSES MIDLINE TOWARD TOY.....             | 0  | 1  | 2  | 3  | 6.  |

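### The GMFM form has a GMFCS severity box, but the plan never says it will be completed, reported by arm, used in allocation or used as a covariate, and no adjustment for severity is prespecified

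*Combined protocol and SAP*

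**What the plan says.** The GMFM score sheet reproduced in Appendix II has tick boxes for GMFCS levels I to V in its header. Its footnote states that "GMFCS level is a rating of severity of motor function". In the body of the protocol the classification appears only in the literature review (4. Gross motor performance), which says that levels of impairment "can be described according to the Gross Motor Classification System".

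Under B. Assessment procedures, the GMFM-88, which is also the gross motor outcome, "will be used to determine the severity of each case".

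GMFCS is absent from the inclusion and exclusion criteria, the list under Data collection and statistical analysis, the demographic sheet (Appendix V) and the outcome sheet (Appendix VI). On allocation, the Sample size calculation section says "the children will be randomly allocated by simple random method via choosing one of two wrapped cards", with no strata or blocks. Under B. Statistical analysis, the baseline summary is "Descriptive statistics (mean and standard deviation) of the demographic data of all patients in both groups". The choice of test is left to the nature of the data, and no model or covariate is named.

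Pre-treatment GMFM-88 and PBS are collected for every child (Delimitations; Appendix VI).

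**The concern.** Severity is likely to be a strong predictor of both outcomes. The literature review says that spastic diplegia "is characterized by a wide range of ambulatory outcomes". The entry rules limit spasticity grade and require stable sitting, but set no limit on walking ability. Most PBS items, and GMFM dimensions D and E, are done standing or walking.

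With 30 children, randomisation balances severity only on average. If the arms differ by chance and the final comparison is the plain t-test on which the sample size was based, part of the estimated effect of virtual reality could be a difference in who was enrolled in each arm. Without GMFCS counts by arm, a reader could judge this only from the baseline outcome scores. A prespecified adjustment would reduce the problem and improve precision at the same time.

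**Working it through.** **1. The plan's own figure.** Inputs from Sample size calculation: t-test, alpha 0.05, effect size 1.135, and 80%, which is worded as a confidence interval but read here as power. Noncentral t, two-sided, noncentrality 1.135 × √(n/2):

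- 13 per arm: 79.3%
- 14 per arm: 82.4%
- 15 per arm: 85.1%

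The smallest n reaching 80% is 14 per arm, so the stated 28 reproduces.

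**2. Chance of a marked split.** Take 30 children with 15 per arm, as the plan intends, and K in the lower-function group. The documents do not give K, so it is assumed. Two-sided hypergeometric probabilities:

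| K of 30 | Split, or worse | Probability |
|---|---|---|
| 6 | 5 v 1 | 16.9% |
| 10 | 7 v 3 | 24.5% |
| 12 | 8 v 4 | 26.4% |
| 15 | 10 v 5 | 14.3% |

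**3. Size of the shift.** For a 10 v 5 split the proportions differ by 10/15 − 5/15 = 1/3. If the two groups' results differ by 0.5 to 1.0 SD (assumed), an unadjusted comparison moves by 0.17 to 0.33 SD. Against the planned effect this is 0.17/1.135 = 15% to 0.33/1.135 = 29%.

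**4. What baseline adjustment leaves.** The GMFM-88 section of the literature review gives "test–retest reliability of 0.88, and intra-rater reliability of 0.68". If true severity is stable and the pre and post scores are equally reliable, the pre–post correlation equals the reliability, rel. Adjustment for the baseline score is then expected to remove a fraction rel of the shift:

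- rel 0.68: 0.32 × (0.17 to 0.33) = 0.05 to 0.11 SD
- rel 0.88: 0.12 × (0.17 to 0.33) = 0.02 to 0.04 SD

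**5. Precision from the baseline score.** With 15 per arm, power is computed from d/√(1 − r²) with one degree of freedom lost; r is assumed. At d = 1.135, 85.1% becomes 88%, 93% and 99% for r = 0.3, 0.5 and 0.7. At d = 0.8, 56% becomes 60%, 68% and 84%.

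**6. What a two-group GMFCS term adds.** Let g be its correlation with true severity. Residual variance after the baseline score is 1 − rel². The further reduction is g²·rel·(1 − rel)² / (1 − g²·rel). If severity is normally distributed, an even two-group split can correlate at most √(2/π) ≈ 0.80 with it. If the full GMFCS scale correlates 0.6 to 0.9 with severity (assumed), the split correlates about 0.48 to 0.72. The power column starts from 80% in the baseline-adjusted model (noncentrality 2.906, 27 error df), divides by √(1 − cut), and uses 26 df.

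| rel | g | Residual variance | Cut | 80% power becomes |
|---|---|---|---|---|
| 0.68 | 0.48 | 0.538 to 0.519 | 3.5% | 81.3% |
| 0.68 | 0.72 | 0.538 to 0.482 | 10.4% | 84.0% |
| 0.68 | 0.80 | 0.538 to 0.459 | 14.5% | 85.7% |
| 0.88 | 0.48 | 0.226 to 0.222 | 1.6% | 80.5% |
| 0.88 | 0.80 | 0.226 to 0.207 | 8.1% | 83.1% |

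These reliabilities are for the GMFM-88. For the PBS the protocol quotes 0.99, and the same model would leave 0.01 × 0.33 = 0.003 SD after baseline adjustment, so the GMFCS term would add almost nothing there. That is the optimistic limit: if children change at different rates, the pre–post correlation falls below the reliability and more is left for GMFCS to explain.

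**The case against.** The strongest objection is that the baseline GMFM-88 and PBS already do this job. They are measured before treatment, are in the dataset, and are legitimate covariates. Baseline-score adjustment would remove most of any shift, so a second covariate in 30 children is hard to justify on bias alone. This largely stands, and it is why the GMFCS term is offered as a small addition. It does not answer the point that the plan commits to no adjustment at all.

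Several stronger readings are tempting, and the documents do not support them:

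- **That GMFCS is recorded for every child and then ignored.** The box is preprinted on a reproduced standard form that also carries GMFM-66 fields. No procedure says it will be completed, so a rating would have to be added.
- **That severity is neither balanced nor adjusted for.** Randomisation balances it in expectation, and the open wording on tests leaves adjustment unspecified, not excluded.
- **That nothing in the dataset would reveal an imbalance.** The pre-treatment scores would partly do so.
- **That taking severity from the GMFM-88 is an error.** A pre-treatment score can describe severity, and the form's footnote does not require this trial to use GMFCS instead.
- **That sitting balance is the only motor entry rule.** Spasticity grade, permanent deformity and limiting orthopaedic disability also restrict entry.
- **That GMFCS could raise power from 80% to 89%.** That needs a correlation of 0.9, which a two-group split cannot reach under normally distributed severity.

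It is also fair to object that one therapist makes all the measurements, so errors in GMFCS and GMFM-88 may be related. That would reduce the gain further.

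**Conclusion.** The concern holds as a cheap improvement of modest size. The plan has a severity field on its form and no stated use for it, no stratification, and no prespecified adjustment for severity or for the baseline scores. A marked severity split has a probability of about 14% to 26%. A 10 v 5 split would matter in an unadjusted comparison (0.17 to 0.33 SD) but much less after baseline adjustment (about 0.02 to 0.11 SD for the GMFM-88).

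Most of the benefit therefore comes from prespecifying the baseline score. A two-group GMFCS term lowers GMFM-88 residual variance by a further 2% to 15% or so, taking 80% power to about 80.5% to 86%.

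These figures rest on an assumed severity mix, an assumed difference between severity groups, assumed GMFCS correlations, stable true severity and independent rating errors. The documents supply only the reliabilities, the arm sizes and the effect size. Reporting GMFCS by arm is worthwhile whatever the gain, because it shows who was enrolled.

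**What to change.** 1. **Assessment procedures and Appendix V:** state that the GMFCS box in Appendix II is completed for every child before the card draw. Add the level to Appendix V and to the list under Data collection.
2. **B. Statistical analysis, item 1:** show GMFCS counts by arm in the baseline table, with pre-treatment GMFM-88 and PBS.
3. **B. Statistical analysis, item 2:** prespecify a between-group linear model for post-treatment GMFM-88 and another for PBS, each adjusted for that outcome's own baseline score, with GMFCS group as a second covariate. Fix the cut between groups in advance; the documents do not support a particular one.
4. **Allocation, only if it is being rewritten:** draw the cards in balanced sets within GMFCS group. The first three items stand without this.

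The sentence that takes severity from the GMFM-88 can stay, and the sample size need not change. The cost is one short rating per child, one data field, a few sentences of protocol text and one degree of freedom for the GMFCS term (26 instead of 27 for error). The optional fourth item needs one more set of cards.

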## GMFM-88 SUMMARY SCORE

| DIMENSION                     | CALCULATION OF DIMENSION % SCORES |   |    |         | GOAL AREA                |                             |
|-------------------------------|-----------------------------------|---|----|---------|--------------------------|-----------------------------|
|                               |                                   |   |    |         | (indicated with ✓ check) |                             |
| A. Lying & Rolling            | Total Dimension A
51           | =   | 51 | × 100 = | _____ %                  | A.  |
| B. Sitting                    | Total Dimension B
60           | =   | 60 | × 100 = | _____ %                  | B.  |
| C. Crawling & Kneeling        | Total Dimension C
42           | =   | 42 | × 100 = | _____ %                  | C.  |
| D. Standing                   | Total Dimension D
39           | =   | 39 | × 100 = | _____ %                  | D.  |
| E. Walking, Running & Jumping | Total Dimension E
72           | =   | 72 | × 100 = | _____ %                  | E.  |
| TOTAL SCORE =          |                                   | $\frac{\%A + \%B + \%C + \%D + \%E}{\text{Total \# of Dimensions}}$                                   |    |         |                          |                             |
|                               | =                                 | _____   | =  | _____   | =                        | _____ %                     |
|                               |                                   | 5   |    |         |                          |                             |
| GOAL TOTAL SCORE =     |                                   | $\frac{\text{Sum of \%scores for each dimension identified as a goal area}}{\text{\# of Goal areas}}$ |    |         |                          |                             |
|                               | =                                 | _____   | =  | _____   | =                        | _____ %                     |

**GMFM-66 Gross Motor Ability Estimator Score **

GMFM-66 Score = \_\_\_\_\_ to \_\_\_\_\_  
95% Confidence Intervals

previous GMFM-66 Score = \_\_\_\_\_ to \_\_\_\_\_  
95% Confidence Intervals

change in GMFM-66 = \_\_\_\_\_

 from the Gross Motor Ability Estimator (GMAE-3) Software

## TESTING WITH AIDS/ORTHOSES USING THE GMFM-88

Indicate below with a check (✓) which aid/orthosis was used and what dimension it was first applied. (There may be more than one).

| AID                    | Dimension                      | Orthosis                 | Dimension                      |
|------------------------|--------------------------------|--------------------------|--------------------------------|
| Rollator/pusher .....  |  _____ | Hip Control .....        |  _____ |
| Walker .....           |  _____ | Knee Control .....       |  _____ |
| H Frame crutches ..... |  _____ | Ankle-foot Control ..... |  _____ |
| Crutches .....         |  _____ | Foot Control .....       |  _____ |
| Quad Cane .....        |  _____ | Shoes .....              |  _____ |
| Cane .....             |  _____ | None .....               |  _____ |
| None .....             |  _____ | Other                    |  _____ |
| Other                  |  _____ | _____                    |                                |
| (please specify)       |                                | (please specify)         |                                |

## GMFM-88 SUMMARY SCORE USING AIDS/ORTHOSES

| DIMENSION                     | CALCULATION OF DIMENSION % SCORES   |   |                       | GOAL AREA                   |
|-------------------------------|---|---|-----------------------|-----------------------------|
|                               |   |   |                       | (indicated with ✓ check)    |
| A. Lying & Rolling            | Total Dimension A   | = | _____ × 100 = _____ % | A.  |
|                               | 51  |   | 51                    |                             |
| B. Sitting                    | Total Dimension B   | = | _____ × 100 = _____ % | B.  |
|                               | 60  |   | 60                    |                             |
| C. Crawling & Kneeling        | Total Dimension C   | = | _____ × 100 = _____ % | C.  |
|                               | 42  |   | 42                    |                             |
| D. Standing                   | Total Dimension D   | = | _____ × 100 = _____ % | D.  |
|                               | 39  |   | 39                    |                             |
| E. Walking, Running & Jumping | Total Dimension E   | = | _____ × 100 = _____ % | E.  |
|                               | 72  |   | 72                    |                             |
| TOTAL SCORE =          | $\frac{\%A + \%B + \%C + \%D + \%E}{\text{Total \# of Dimensions}}$                                   |   |                       |                             |
|                               | =   |   | _____ = _____ %       |                             |
|                               |   | 5 |                       |                             |
| GOAL TOTAL SCORE =     | $\frac{\text{Sum of \%scores for each dimension identified as a goal area}}{\text{\# of Goal areas}}$ |   |                       |                             |
|                               | =   |   | _____ = _____ %       |                             |

## Appendix III

### Pediatric Balance Scale (PBS)

A

#### PEDIATRIC BALANCE SCALE

Name: \_\_\_\_\_ Date: \_\_\_\_\_  
 Location: \_\_\_\_\_ Examiner: \_\_\_\_\_

| Item Description                    | Score
0 - 4 | Seconds
optional |
|--|-----------------------|-----------------------------------|
| 1. Sitting to standing                     | _____                 |                                   |
| 2. Standing to sitting                     | _____                 |                                   |
| 3. Transfers                               | _____                 |                                   |
| 4. Standing unsupported                    | _____                 | _____                             |
| 5. Sitting unsupported                     | _____                 | _____                             |
| 6. Standing with eyes closed               | _____                 | _____                             |
| 7. Standing with feet together             | _____                 | _____                             |
| 8. Standing with one foot in front         | _____                 | _____                             |
| 9. Standing on one foot                    | _____                 | _____                             |
| 10. Turning 360 degrees                    | _____                 | _____                             |
| 11. Turning to look behind                 | _____                 |                                   |
| 12. Retrieving object from floor           | _____                 |                                   |
| 13. Placing alternate foot on stool        | _____                 | _____                             |
| 14. Reaching forward with outstretched arm | _____                 |                                   |
| Total Test Score                    | _____                 |                                   |

